6.1.2.4 API weekly responder based on actual randomization

The stratified strata is based on the baseline abdominal pain score which is the average from 7 days immediately prior to the baseline visit. If more than 10% mis-classification of the stratification factors (randomization stratification vs. actual stratification values) happens a sensitivity analysis of the primary analysis will be carried out to repeat the primary analysis where the actual stratification will be used in the model.

6.1.3. Subgroup Analysis

The CMH estimate of treatment difference for API weekly responder with $\geq 30\%$ improvement over Weeks 1-12 will be prepared for each of stratified strata (abdominal pain intensity score <6 vs ≥ 6) based on the FAS.

In addition, the proportion of responder will be summarized by the following three subgroups.

- Age category (<40, ≥ 40 to <65, ≥ 65 years)
- Race (as recorded in CRF)
- Subjects randomized prior to 31Dec2019 vs Subjects randomized after 31Dec2019
- Baseline Bristol Stool Scale (< 5.5 vs ≥ 5.5)

[figure not shown]
6.2. Secondary Efficacy Analyses

[figure not shown]
The secondary efficacy endpoint GIS responder at Week 12 is defined in [Section 4.3.1](#). The proportion of responders will be analyzed similarly as described for primary endpoints using CMH for IBS-D and IBS_M subjects. When all subjects are included for the analysis, additional IBS subtype (IBS-D vs. IBSM will be used for stratification as well. The number and percentage of responder and non-responder for IBS-D, IBS-M and all IBS subjects will be tabulated by treatment and visit. GIS response data will be listed.

[figure not shown]
The secondary efficacy endpoints of proportion of IBS-D subjects who are API weekly responders with 40% improvement and API weekly responders with 50% improvement from Week 1 through Week 12 are defined in the [Section 4.3.1](#). The similar statistical analyses described in primary efficacy endpoint will be performed for these API weekly responders including subgroup analysis.

[figure not shown]
The secondary efficacy analyses will be primarily based on the FAS, unless stated otherwise.

6.3. Exploratory Efficacy Analysis

A large black rectangular box covers the majority of the page below the section header, indicating that the content has been redacted.

7. SAFETY ANALYSIS

The SAF will be used for all safety analyses. Safety will be assessed on the basis of extent of exposure and compliance, AE reports, clinical laboratory data, ECGs, physical examinations, and vital signs.

No inferential statistical testing is planned on the safety data, all data will be descriptively summarized by treatment and visit.

7.1. Extent of Exposure

The duration of exposure during the double-blind treatment period will be expressed as the time in days from the first dose as recorded on the Study Drug Administration CRF page at Visit 3 through to last treatment day (inclusive) as recorded on the End of Treatment CRF

page, excluding any days where it is recorded that an interruptions has occurred on the AE CRF page and as indicated on the COVID19 CRF page.

Interruption in days = date started – date stopped + 1

This is given by the following formula:

Duration (days) = date last double blind dose – date first double blind dose – interruption days + 1

Duration of exposure will be summarized by treatment group for the SAF using summary statistics for continuous variables. The proportion of subjects with Dose Interruptions ≥ 2 weeks (14 consecutive days) will be summarized by treatment group, if applicable.

A listing will present the treatment start and end date together with the date of interruption, and the overall days of exposure.

7.2. Treatment Compliance

Study treatment compliance (%) will be calculated as the actual number of doses divided by the expected number of doses, multiplied by 100 and summarized by treatment group for double-blind treatment period

These numbers will be determined by the number of tablets dispensed and returned unused by the subject. Where no treatment bottle is returned, and thus the actual number of doses is unknown, it will be assumed that the subject took all medication available in the bottle. The overall compliance will be calculated for double-blind treatment period, respectively.

$$\text{Overall Compliance (\%)} = \frac{\text{Number of total tablets taken}}{\text{Target number of total tablets dispensed}} \times 100\%$$

The number of tablets taken is obtained by: (no. dispensed – no. returned). The target number of tablets to be taken is calculated as: (last dose date – first dose date – drug interruption in days + 1). Partial dates will be imputed if the day of the month is missing as described in [section 4.2.3](#). However, if month and/or year are missing for the date of last dose then date of last dose will be assigned the study discontinuation date. Treatment Compliance will be summarized by treatment group and overall for the SAF population. Additionally, the number and percentage of subjects within each treatment with compliance in the following categories will be provided: <80%, 80 – 120%, and >120%. A listing will present compliance data, including bottle number of tablets dispensed, returned, and dispensed and returned dates and overall compliance.

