6.1. Study Drugs Administered

Study Drug Name	Vibegron	Matched Placebo
Dosage Formulation	tablet	tablet
Identity of Formulation	75 mg	placebo
Route of Administration	oral	oral
Dosing Instructions	once daily	once daily
Packaging and Labeling	Study drug will be provided in HDPE bottles with child resistant caps. Each bottle will contain 32 tablets and will be labeled as required per country requirement.	Study drug will be provided in HDPE bottles with child resistant caps. Each bottle will contain 32 tablets and will be labeled as required per country requirement.
Manufacturer	Patheon, Cincinnati, Ohio, US	Patheon, Cincinnati, Ohio, US
Number and Timing of Drugs	Treatment Period: 1 tablet daily	Run-in Period: 1 tablet daily Treatment Period: 1 tablet daily

HDPE = high density polyethylene

The study drug will be supplied in bottles each containing 32 tablets (4-week supply) and labeled with the protocol number, bottle number, lot number, expiration date, study drug name (vibegron 75 mg or placebo tablets), number of tablets, directions for use, storage information, warning language (*Keep Out of Reach of Children. For Clinical Trial Use Only. To be used by qualified Investigators only. Caution: New Drug—Limited by United States Law to Investigational Use.*), and the US Sponsor name and address. Immediately before dispensing the study drug, the Investigator (or appropriately trained designee) will write the subject number, visit number, and the dispense date on the detachable panel of the label, which also includes the protocol number, bottle number and lot number.

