3.2.1. Protocol Deviations

The final list of major protocol deviations will be finalized and documented prior to database lock except for the deviation category of wrong treatment which will be confirmed upon study unblinding. Only major (i.e., significant per the protocol deviation plan) protocol deviations will be summarized and listed in the Clinical Study Report (CSR). Major deviations will be those which are considered to potentially impact upon the interpretation of the primary efficacy endpoint in the study or may potentially impact the interpretation of safety. Major protocol deviations may include, but are not limited to the following:

- Randomized subjects who do not meet the inclusion criteria
- Randomized subjects who meet any of the exclusion criteria
- Subjects who received the wrong treatment
- Concomitant use of prohibited medications
- Randomized subjects who met withdrawal criteria during the study but were not withdrawn
- Subjects whose IP was interrupted 14 consecutive days or more during the double-blind treatment period OR had IP compliance less than 80% from Weeks 8-12
- Subjects who were not compliant in study procedures (e.g., if 3 or more days of diary entry were missed between visits that were a 2-week period or if 6 or more days of diary entry missed between visits that were a 4-week period)

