11.1.3. Output Listings

Table 8: List of Output Listings

Title		Population	Programming Note	Deliverable
Disposition and Demographics				
16.2.1.1	Subject Disposition for Screen Failures	Screened		EOS

Title		Population	Programming Note	Deliverable
16.2.1.2	Run-In Treatment Administration	Placebo Run-In Set		EOS
16.2.1.3	Subject Disposition	Randomized		EOS
16.2.1.4	Subjects who did not Satisfy Inclusion/Exclusion Criteria	Screened		EOS
16.2.1.5	Subject Randomization Details	Randomized		EOS
16.2.1.6	Major Protocol Deviations	Randomized		EOS
16.2.1.7	Subject Demographic and Baseline Characteristics	Randomized		EOS
16.2.1.8	Medical History	Randomized		EOS
16.2.1.9	Prior and Concomitant Medications	Randomized		EOS
16.2.1.10	Prior Irritable Bowel Syndrome (IBS) Medications	Randomized		EOS
16.2.1.11	Additional Rescue Concomitant Medication information	Randomized		EOS
16.2.1.12	Subjects with Misclassification of Stratification Factors	Randomized		EOS
16.2.1.13	COVID-19 Impact	All Subject	include treatment IBS subtype and all the information collected on COVID-19 eCRF	EOS
Efficacy				EOS
16.2.2.1	Weekly API Responder	FAS	Sort by Treatment, IBS Subtype, Subject ID, Baseline API Strata, Week	TL
16.2.2.2	Global Improvement Scale Responder Classification	FAS		EOS
16.2.2.3	Derived Parameters from Bowel Movement Diary	FAS	Sort by Treatment, IBS Subtype, Subject ID, Baseline API Strata	EOS
16.2.2.4	Additional Abdominal Pain Questionnaires	FAS		EOS
16.2.2.5	Additional IBS-related Baseline Data			
16.2.2.6		FAS		EOS

Title		Population	Programming Note	Deliverable
16.2.2.7	[REDACTED]	FAS		EOS
16.2.2.8	Missing Diary Days	FAS		TL
16.2.2.9	Cumulative Weekly API Responder	FAS	Sort by Treatment, IBS Subtype, Subject ID, Baseline API Strata	TL
16.2.2.10	[REDACTED]	FAS	Sort by Treatment, IBS Subtype, Subject ID, Baseline API Strata	TL
16.2.2.11	[REDACTED]	FAS	Sort by Treatment, IBS Subtype, Subject ID, Baseline API Strata	TL
16.2.2.12	Cumulative Daily API Responder	FAS	Sort by Treatment, IBS Subtype, Subject ID, Baseline API Strata	TL
16.2.2.13	[REDACTED]	FAS	Sort by Treatment, IBS Subtype, Subject ID, Baseline API Strata	TL
Safety				
16.2.3.1.1	Treatment Exposure and Compliance	SAF		EOS
16.2.3.1.2	Subjects with Compliance > 120% who Were Not Lost to Follow-Up	SAF	To identify any subject with >> 120% compliance who was not lost of follow-up	EOS
16.2.3.2.1	Adverse Events	SAF		EOS
16.2.3.2.2	TEAE Serious Adverse Events	SAF	Use the vertical format	EOS

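### Counting every tablet in an unreturned bottle as taken gives implausible compliance for women lost early and can hide poor intake from the third bottle

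*SAP*

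**What the plan says.** SAP 7.2 defines overall double-blind compliance as tablets taken (dispensed minus returned) over a target of "last dose date – first dose date – drug interruption in days + 1". If a bottle is not returned, "it will be assumed that the subject took all medication available in the bottle". If the month or year of the last dose is missing, the "date of last dose will be assigned the study discontinuation date". Compliance is summarised for the Safety Analysis Set as a continuous variable and in three bands: below 80%, 80 to 120%, and above 120% (Table 14.3.1.2).

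Protocol 6.1 gives the bottle content as "32 tablets (4-week supply"), one tablet daily. Double-blind bottles are dispensed at Day 1, Week 4 and Week 8 (Protocol 1.3).

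Compliance appears in two other places in the SAP:

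- Listing 16.2.3.1.2 is meant to find any subject well above "120% compliance who was not lost of follow-up".
- SAP 3.2.1 names as a possible major deviation a subject who "had IP compliance less than 80% from Weeks 8-12", or whose study drug was interrupted for at least 14 consecutive days. Important deviations determine the per-protocol set for IBS-D, PPS-D (SAP 3.1.6).

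**The concern.** The SAP acknowledges that intake is unknown when a bottle is missing, then assigns the largest value it could take. The women with the least evidence of intake are shown as fully compliant or over-compliant. SAP 4.2.3 takes the opposite line elsewhere: missing safety data are in general not imputed, and missing adverse event severity or relationship is filled in conservatively.

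Two outputs are at stake. The mean and the >120% category of Table 14.3.1.2 mix real over-use with lost bottles. The Protocol itself treats intake above 120% during run-in as noncompliance (exclusion criterion 38), so this category carries meaning. The second output is PPS-D: if the convention carries over to Weeks 8-12, poor intake from a third bottle that was kept would not trigger the below-80% criterion.

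**Working it through.** The documents state no compliance figure to reproduce, so the check applies the SAP 7.2 formula directly.

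**Inputs.** 32 tablets per bottle (Protocol 6.1); one tablet daily; bottles dispensed at Day 1, Day 29 and Day 57, with ± 4 days on the post-baseline visits (Protocol 1.3). Assumed: no recorded interruption, and 28 tablets taken from each returned bottle.

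**Step 1: overall compliance when the last bottle held is missing.** Compliance = 100 × tablets counted / last dose day. It exceeds 120% while the last dose day is below tablets counted / 1.2.

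| Missing bottle | Tablets counted | Above 120% up to | Examples |
|---|---|---|---|
| 1 | 32 | Day 26 (32/1.2 = 26.7) | Day 10: 320%; Day 21: 152% |
| 2 | 28 + 32 = 60 | Day 49 (60/1.2 = 50.0) | Day 35: 171% |
| 3 | 56 + 32 = 88 | Day 73 (88/1.2 = 73.3) | Day 63: 140%; Day 66: 133% |

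With bottle 1 missing and a last dose before Day 16, the implied average is above 2 tablets a day (32/15 = 2.13).

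**Step 2: completers who under-dose from an unreturned bottle 3.** The target is 84 days.

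- Half of the last 28 doses taken: recorded (56 + 32)/84 = 104.8%; true (56 + 14)/84 = 83.3%.
- None taken from bottle 3, last dose date still recorded as Day 84: recorded 104.8%; true 56/84 = 66.7%.

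If at most one tablet a day was taken, the returned bottles support only a range of 56/84 = 66.7% to 84/84 = 100%. The SAP's single value lies above it.

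**Step 3: the Weeks 8-12 criterion, if SAP 7.2 is applied to bottle 3.** A count of 32 falls below 80% only when the target exceeds 32/0.80 = 40 days. The longest Week 8 to Week 12 interval that the windows allow is Day 53 to Day 89, or 36 days, giving 32/36 = 88.9%. Over 28 days the result is 32/28 = 114.3%, whether true intake was 0% or 100%.

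**Step 4: where the floor fails.** With bottle 1 missing and the last dose date replaced by a later discontinuation date, compliance is 32/41 = 78.0% at Day 41 and 32/60 = 53.3% at Day 60. Overall compliance can also fall below 80% for a completer without bottle 3 if the first two bottles show 35 or fewer tablets taken: (35 + 32)/84 = 79.8%.

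**Step 5: shift in the mean, illustrative only.** Assume that 5% to 10% of women have a 133.3% value of the kind in Step 1. If their true compliance is 100%, as daily dosing to Day 66 would imply, the mean rises by 0.05 × 33.3 = 1.7 to 0.10 × 33.3 = 3.3 points. If it is 90%, the rise is 0.05 × 43.3 = 2.2 to 0.10 × 43.3 = 4.3 points. The documents give no non-return rate; Protocol 9.2 assumes only 10% discontinuation for any reason.

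**The case against.** The strongest reply is that little depends on this. Compliance is descriptive, PPS-D is supportive, and FAS-D follows randomized treatment regardless of intake. The sponsor foresaw the artefact: there is a separate >120% band, Listing 16.2.3.1.2 picks out high values not explained by loss to follow-up, and the compliance listing shows tablets dispensed and returned. Medians and quartiles resist a few outliers. Sites must try to recover bottles (Protocol 6.4), and the first bottle is checked at Week 2. Most of this stands and limits the importance. It does not repair Table 14.3.1.2, which has no matching separation.

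On PPS-D, SAP 3.2.1 gives no formula for Weeks 8-12, so carrying over the Section 7.2 convention is an inference. The same bullet catches a recorded interruption of 14 days or more, the deviation list is open-ended, and membership is settled before unblinding. These points also stand. Scattered or unrecorded missed doses would still escape the interruption limb.

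Treating the interval as unknown does not recover the truth either. The half-taker in Step 2 becomes 56/56 = 100%, against a true 83%. That is correct, and it is why the number of unreturned bottles has to be reported alongside.

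A reader might infer that a non-returner can never fall below 80%, or that figures such as 114% for a single bottle will appear in the report. Neither follows. Step 4 shows the exceptions, a postponed visit could add another, and SAP 7.2 plans only an overall percentage.

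**Conclusion.** The rule as written produces wrong values, so this is more than a missing detail. Women lost with a bottle outstanding are reported above 120% for any last dose up to Day 26 (bottle 1) or Day 73 (bottle 3, with 56 tablets taken earlier). A completer who took half of a retained third bottle is overstated by 104.8 − 83.3 = 21.5 points. These values enter Table 14.3.1.2, and Listing 16.2.3.1.2 does not remove them.

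The PPS-D consequence is conditional on SAP 7.2 also defining Weeks 8-12 compliance and on visits within the protocol windows. The shift in mean compliance depends on an assumed non-return rate. A reader might also infer a biased comparison between arms or a threat to the primary result. The documents give no reason to expect non-return to differ by arm, and the primary FAS-D analysis does not use compliance. The point is modest in consequence and inexpensive to correct.

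**What to change.** Make three changes:

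1. **SAP 7.2.** Replace the sentence on unreturned bottles: the interval covered by such a bottle is treated as unknown and left out of both numerator and denominator.
2. **Table 14.3.1.2.** Add a row with the number of subjects with at least one unreturned bottle in each arm.
3. **SAP 3.2.1.** State that a subject whose third bottle was not returned has unknown Weeks 8-12 compliance, is not counted as compliant, and goes to the deviation review already planned before unblinding.

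The cost is a few sentences and one table row. Some compliance values become missing, including those of women lost with only the first bottle dispensed. The remaining summary describes returned bottles only, so the count row is a necessary part of the change.

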4.2.3. Premature Withdrawal and Missing Data

All data collected in the study database after the subject's early withdrawal of study treatment should be included in summary and analysis.

If any missing data are present in diary data for any reasons, no imputation will be applied to derive responder since the minimum compliance rules described in responder definition in [Section 4.3.1](#) accounted for missing diary entries. No explicit missing data imputation will be performed for change from baseline since a mixed model for repeated measures (MMRM) will be applied to change from baseline analysis. Missing items from the subject reported outcomes (PROs) will be handled according to the respective measure instructions as described in [Section 4.3.2](#).

In general, missing safety data will not be imputed and only observed values will be analyzed. Data of subjects who withdraw after the screening examination or are not treated will be only listed.

If the relationship of an AE record (“Relationship to investigational product” on AE CRF) is missing this AE will be considered “Probably Related” to the study treatment. If the AE intensity is missing every effort should be made to acquire the information from the investigator. “Severe” will be assigned to a missing intensity for reporting purpose

The general imputation rules of partial missing date for both AE and concomitant medication is detailed below:

Dates missing only the day of the month within a year will adhere to the following conventions:

- The missing day of onset date will be set to:
 - First day of the month that the event occurred, if the onset YYYY-MM is after the YYYY-MM of first double-blind treatment
 - The day of the first run-in treatment, if the onset YYYY-MM is the same as YYYY-MM of the first run-in treatment, but different from YYYY-MM of the first double-blind treatment
 - The day of the first double-blind study treatment, if the onset YYYY-MM is the same as YYYY-MM of the first double-blind treatment and the first single-blind treatment
 - The date of informed consent, if the onset YYYY-MM is before the YYYY-MM of the first single-blind treatment.
- The missing day of end date will be set to:
 - The last day of the month of the occurrence. If the subject died in the same month, then set the imputed date as the death date.

Dates missing both the day and month of the year will adhere to the following conventions:

- Missing day of onset date will be set to:

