5. DEMOGRAPHIC, OTHER BASELINE CHARACTERISTICS AND MEDICATION

5.1. Subject Disposition and Withdrawals

Subject disposition will be summarized by treatment group for the Screened, Run-in and Randomized Sets separately. The summary table will present the frequency and percentage of subjects in each of the analysis sets and those who discontinued the study prematurely along with the primary reasons for discontinuation.

For the summary under the Randomized Set, the following additional categories will be presented as well; randomized, received treatment with study drug, did not receive treatment with study drug, completed treatment with study drug, discontinued treatment with study drug (and reason), and withdrawn from study (and reason).

The frequency and percentage of subjects with at least one major Protocol Deviation (PD), major PD by classification and reasons/category for PD will be summarized by treatment arm and by FAS-D, FAS-M and FAS. Inclusion in each of the analysis sets (SAF, FAS, FAS-D, etc.), and any reasons for exclusion will be summarized by treatment arm for the Randomized Set.

Screen Failure, Run-in and Double-Blind Period disposition, with reasons for discontinuation of study will also be listed, including the date of discontinuation and date of last contact. The date of last contact is the maximum date of study discontinuation, follow-up or the return of study medication. When lost to follow-up, the latest date of assessment/event in the database will be used as the last known date of the subject in study.

Eligibility criteria, screening and run-in failures (including date and primary reason for failure), and informed consent (protocol version, informed consent version date and date signed) will be listed for all subjects screened.

A summary of randomized subjects by country, investigator name and site identification will be provided.

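### SAP 7.2 sets a last-dose date with only the day missing to month-end, uncapped at study exit, which biases overall compliance downward

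*SAP*

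**What the plan says.** SAP 7.2 (Treatment Compliance) takes the tablets taken as those dispensed minus those returned, and the target number as "last dose date – first dose date – drug interruption in days + 1". The last-dose date thus enters the denominator only.

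For incomplete dates, SAP 7.2 has two rules:

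- **Only the day missing.** "Partial dates will be imputed if the day of the month is missing as described in" Section 4.2.3. The rules there are introduced as follows: "The general imputation rules of partial missing date for both AE and concomitant medication is detailed below". For an end date with a missing day, the value is "The last day of the month of the occurrence". The single exception reads: "If the subject died in the same month, then set the imputed date as the death date".
- **Month or year missing.** "However, if month and/or year are missing for the date of last dose then date of last dose will be assigned the study discontinuation date".

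Protocol 7.2 says that a woman who stops double-blind study drug also withdraws from the study. SAP 7.2 reports compliance as <80%, 80–120% and >120%, and counts every tablet in an unreturned bottle as taken.

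**The concern.** An imputation rule written for adverse events and concomitant medication is borrowed for a dosing date. A late end date may be a cautious choice for those records. For a last dose it adds days to a denominator.

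Two things mark this as an error and not a convention. First, the rule can produce an impossible date: under Protocol 7.2 no dose should follow study exit, yet nothing stops the imputed date at discontinuation. Second, the two rules in SAP 7.2 pull against each other. A date that lacks the month is bounded at study exit, while a date that lacks only the day is not, so the better-documented record can get the less plausible value.

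What is at stake is the compliance table: a woman who took every tablet until she stopped can be reported as under 80% compliant.

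**Working it through.** The documents give no figure to reproduce, so the check applies the SAP's own formulas to assumed dates.

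**Formulas (SAP 4.2.3 and 7.2)**

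- Imputed last dose = last calendar day of the recorded month.
- Target tablets = last dose − first dose − interruption days + 1.
- Compliance = tablets taken / target tablets × 100.

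**Worked example (assumed dates).** First dose 10 Feb 2020 (Day 1), no interruption, true last dose 3 Apr 2020, study exit 6 Apr 2020, 54 tablets taken. The day count is 29 Feb = Day 20, 31 Mar = Day 51, 3 Apr = Day 54, 6 Apr = Day 57, 30 Apr = Day 81.

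| What is recorded | Last dose used | Target | Compliance |
|---|---|---|---|
| Full date | 3 Apr | 54 | 54/54 = 100% |
| Day missing | 30 Apr | 81 | 54/81 = 66.7% |
| Month also missing | 6 Apr | 57 | 54/57 = 94.7% |

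The month-end date lies 81 − 54 = 27 days after the true last dose and 81 − 57 = 24 days after study exit. The target is inflated by 81/54 = 1.50.

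**How general this is.** Let D be the true days on drug and e the added days. For a woman who took one tablet a day, with no interruption and all bottles returned, reported compliance is D/(D + e). It falls below 80% when e > D/4. Running the true last dose through each of the 366 days of 2020 gives e from 0 to 30, mean 14.8, and above 0 on 97% of dates.

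| D | Smallest e giving <80% | Mean compliance | Lowest | Share of dates giving <80% |
|---|---|---|---|---|
| 14 | 4 | 54% | 32% | 87% |
| 28 | 8 | 68% | 48% | 74% |
| 56 | 15 | 80% | 65% | 51% |
| 84 | 22 | 86% | 74% | 28% |

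True compliance is 100% in every row. The shares treat all calendar dates as equally likely and apply only to women whose last-dose day is missing. The proportional error is largest in early stoppers, but a woman with 84 days on drug is not immune.

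**Effect of a cap at study exit.** In the example the capped date is 6 Apr, giving 94.7%. A second assumed case: first dose 5 Feb 2020, true last dose 3 Mar (28 days, 28 tablets), exit 5 Mar. The current rule gives 31 Mar and 28/56 = 50%. The cap gives 5 Mar and 28/30 = 93.3%.

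**The case against.** The best case for leaving this alone is that little depends on it, and most of that case stands.

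- **Exposure.** A reader might infer that early stoppers are also credited with days on drug that they did not have. The documents do not say so. SAP 7.1 takes the last treatment day as recorded on the End of Treatment CRF page and does not refer to the imputation rules. Overstated exposure follows only if the imputed date is carried over, which the SAP leaves unstated.
- **Adverse events.** A later last dose would extend the 14-day treatment-emergent window, in the example to 14 May instead of 17 Apr. Protocol 8.4.1 collects events only to 14 days after the last dose, so the added stretch is nearly empty. The exception is a late related serious event that the investigator happens to learn of.
- **Week 12 windows.** The imputed Day 81 passes the Day 71 condition in SAP 4.2.4.2, but the example woman has no assessment after Day 57 to be moved.
- **Per-protocol set.** SAP 3.2.1 lists compliance below 80% in Weeks 8–12 as a possible major deviation. That differs from overall compliance, and no formula ties it to this date.
- **Frequency.** Nothing says how many last-dose dates will be partial, or in whom. The planned 10% discontinuation rate is not a bound, since completers can have partial dates too. Protocol 6.4 and 10.1.8 require dosing and treatment-end dates to be recorded.
- **Unreturned bottles.** Counting their tablets as taken pushes compliance up. With two unreturned 32-tablet bottles, the example gives 64/81 = 79.0% with the imputed date and 64/54 = 118.5% with the true one. One error partly hides the other; neither is corrected.

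Reading the last dose as an end date is itself an inference, but the onset rules in SAP 4.2.3 make no sense for it. None of these points answers the contradiction within SAP 7.2 or the possibility of a dose dated after study exit.

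**Conclusion.** Wrong as written, minor. When only the day of the last dose is missing, the stated rule can place the last dose after study exit and up to 30 days after the true date, and can only push overall compliance down relative to the true date. A fully adherent woman can be moved from 100% to the <80% category.

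The established effect is on one descriptive summary, in a safety section with no planned inferential testing (SAP 7). The primary FAS-D analysis does not use compliance and is untouched. Effects on exposure, on windows defined as last dose + 14 days, or on the per-protocol set are conditional on the same imputed date being used there, and the documents do not establish that. The size in practice depends on the unknown number of partial dates and is probably small.

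**What to change.** Replace the day-missing rule in SAP 7.2 with: if only the day of the last dose is missing, use the earliest of the last day of the recorded month, the study discontinuation date and the death date, but not before the first day of the recorded month or the first double-blind dose. State that this one derived date is used wherever a last-dose date appears, including SAP 7.1 and the last dose + 14-day periods. The sentence should also name the date that stands in for discontinuation in women who complete.

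Two additions that look natural should be left out. SAP 5.1 says: "The date of last contact is the maximum date of study discontinuation, follow-up or the return of study medication". Being a maximum that includes discontinuation, it can never be the earliest of the candidates. The latest date in the database, which SAP 5.1 uses for women lost to follow-up, could precede the recorded month. For example, a last entry on 20 Mar with a last dose recorded only as April would contradict the record and make compliance falsely high.

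The cost is one sentence and one line of derivation code. A small overstatement remains when exit comes a few days after the last dose: 3 days in the first example and 2 in the second.
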